Subjects will initially be screened over the phone. They will then be emailed the consent form to read and scheduled for a consent appointment over zoom, where they will be taken through the consent procedure with a research coordinator and given time to ask questions. Consent will be proved using Docu-sign. Participants will then be scheduled for an appointment at the CRC where they will provide a baseline blood draw, HCG urine test and urine toxicology. An EKG test will also be performed. If a stay at home order is in place, subjects will be required to provide a current EKG (within the last three months) as well as the last blood pressure reading from their most recent primary care physician visit. If they are unable to provide this, they will be waitlisted until they are able attend the CRC. All questionnaires and clinical interviews (including the SCID) will be performed over ZOOM by virtual visit. All clinical testing will be reviewed by the study physician ([name]).

If the subject proves to be in good health (as confirmed with the study physician) and meets study inclusion / exclusion criteria, a package will be sent out in the mail by UPS. The package will contain a blood pressure monitor kit, urine toxicology cups, disposable breathalyzers for alcohol and 1 week of medication (dose determined by week in study)

timeline calendar, blood pressure heart rate daily log, and written instructions on how to perform these tests.

INTAKE 2: Intake 2 will be conducted early in the morning in order to ensure that the initial medication dose is as close to 8am as possible.

Once the package is received by the participant, the second intake will be performed over virtual media (ZOOM). The subject will first meet briefly with the study physician in order to establish good health. The subject will then meet with the study RA to complete questionnaires, the timeline follow back and take a tutorial on how to use the blood pressure monitor. All subjects will also provide a urine sample to assess drug use by taking a photo of the test strip on the urine cup using their cell phone, and sending it to the study site cell phone to be printed and stored in the participant binder.

Disposable breathalyzer tests will additionally be completed and logged in the participant binder and results displayed via zoom.

Participant will then administer the first dose of study medication or virtual media visit. Questionnaires and surveys will be conducted and timeline follow back will be obtained. Sit stand blood pressure recordings will be taken at the end of this intake. Appointment for the weekly virtual visits will be scheduled.

Medication

At a second intake appointment participants will meet with the study MD, and once cleared begin the first dose of Guanfacine or placebo. They will be randomly assigned to either GXR (3mgs) or PLA, and will receive the exact amount of medication until their next visit, provided in unit/dose containers and labeled with the time and date to facilitate appropriate dosing. Riboflavin will be added to the medications and blood plasma assessed for medication levels every four weeks to ensure compliance¹³¹. The use of extended release GXR will also necessitate the use of only 1 tablet per day, increasing likelihood of adherence

ALL SESSIONS:

SAFETY GUIDELINES FOR THE COVID-19 VIRUS DURING:

WEEKLY STUDY VISITS 2 x per week – all virtual:

All assessments will be performed by virtual visit over a secured media site. Using ZOOM with end to end encryption. Subjects will be mailed via UPS with signature required: 1 BP monitoring kit, Urine toxicology cups, 1-week medication until titrations to the optimal dose of 3 mg of Guanfacine or Placebo; based on the blind randomization assigned by the pharmacist. Subjects will receive virtual tutorials from the research staff on the use of the BP monitor and utilization of the urine toxicology cups through zoom. Subjects will be monitored via virtual media during the use of these tools each visit. All adverse events to be reported and documented during these visits. Reported to study MD as needed and virtual visit with MD as needed. All SAFTEE documents will be administered and documented. One virtual visit each week will include medication management, with continued assessment of the subject during the COVID_19 crisis to insure that additional counseling is not needed.

Weekly Assessments include the following:

1. SAFTEE sheet – documenting any adverse effects

2. A series of short rating scales measuring: craving (AUQ), stress (PSS), emotion regulation (DERS), mood (POMS), anxiety (STAXI), depressive symptoms (BDI) and withdrawal symptoms (CIWA)
3. Timeline follow back (TLFB) – subject report of daily alcohol/drug use
3. Vitals – sitting to standing
4. Urine toxicology screens and breathalyzer. At week 4 and week 8 participants will also take a pregnancy test
5. All participants will additionally be required to obtain a blood draw at the CRC on week 4 and week 8 in order to assess LFTs, glucose and CBC and to quantify medication levels.

Procedures

Outpatient procedures: All AUD women will be required to attend two outpatient visits per week for 10-weeks. All women will take part in Medical Management (MM) and Contingency Management (CM) protocols. All clinicians will be fully trained in these procedures, and educated specifically in the treatment needs of women, including relationship issues, caregiving status, anxiety, mood and eating¹³². In week 10 of treatment a 12-day taper schedule will be implemented¹³³, prior to discharge

Dosing: Dosing will begin at Intake 2 appointment. Women receiving GXR will begin dosing at 1 mg/d (days 1-7). Dosages will escalate to 2mg/d (days 7-21) and 3mg/g (day 21- onwards). Please see Appendix 5 for titration and updated taper schedule. Identical placebo tablets will be used. All guanfacine and placebo tablets will contain riboflavin in order to ensure compliance

Medical management (MM) & contingency management (CM) for treatment adherence: The primary focus of the MM protocol¹³⁴ is to assist clinicians in providing educational support strategies for maintaining medication adherence. It was designed for delivery in a primary care setting and as such is a suitable platform for use in outpatient clinical trials assessing new medications for alcohol¹³⁵¹³⁷. Primary goals include promoting compliance via psycho-educational methods as well as encouraging participation into self-help programs aimed at women¹³⁴. The initial session will be 3045 minutes followed by 10 minute follow-up sessions once per week. In addition, all subjects will receive CM providing participants with the opportunity to increase chances of winning variable dollar prizes at study completion for kept appointments. See Human Studies Section for full details of gender-specific recruitment goals (1.2) & CM protocol (4.1.3). **3.5.3 Outpatient Assessments:** Primary Outcomes: All participants will be required to provide a urine and breathalyzer screen at each appointment. In addition, the Time-Line Follow-Back Interview¹³⁰ will be used to assess all alcohol and nicotine use in the previous 90 days at baseline and weekly during the 10 week treatment trial. Primary alcohol use outcomes will be: (1) time to initial drink and heavy drinking (men: ≥ 5 drinks; women: ≥ 4); (2) frequency: the total number of days of alcohol use; and (3) quantity: the average amount of alcohol use (no. of drinks) per occasion. Subjects will be considered drop-outs if they receive two phone calls and two letters inviting them to return. We will attempt to assess these early terminators at the time of discontinuation, at the 10 week termination point, and at the follow-up period. These women will be withdrawn from the study but considered in the intent-to-treat efficacy analyses. Secondary Outcomes: The following measures will be administered upon admission and twice weekly to assess the effects of GXR on craving, anxiety, mood, stress and regulation: AUQ; STAI; BDI; POMS-Bi; PSS; DERS; BIS-11 and Stroop. Data Safety: The following measures will be assessed: (i) Sitting and standing vital signs: every 15 minutes for one hour (ii) Liver function tests, glucose and Complete Blood Count (CBC): weeks 4 and 8 for abnormal values (iii) Systematic Assessment of Treatment Emergent Events (SAFTEE): every week to assesses the severity and duration of potential physical or health problems. Adverse events will be documented according to the criteria outlined in the Human Subjects section 6.0. (iv) Blood draw to assess

medication levels: weeks 4 and 8 (v) urine test to ensure the participant is not pregnant: weeks 4 and 8.

SAFETY GUIDELINES FOR THE COVID-19 VIRUS DURING:

LAB SESSIONS:

Safe distancing practices to be implemented during the pandemic crisis. NO stress challenge labs will be initiated until the STATE OF NEW YORK is cleared by the CDC, or NIH from this current DISASTER CRISIS.

Laboratory Session: The laboratory challenge session will be conducted in the 10th week of outpatient treatment, when all participants have reached full dose. During the lab, subjects will be brought into the testing room at 1 PM following a smoke break to control for nicotine withdrawal if needed. A cotton ball will be placed inside the mouth to collect saliva, a blood pressure cuff and pulse oximeter used to periodically monitor vitals. After 10 minutes relaxation, baseline measures of alcohol craving, nicotine craving, anxiety, mood, HRBP and saliva will be collected -5 minutes prior to imagery exposure. Subjects will then be given headphones and asked to imagine the situation being described, 'as if' they were actively participating in it at that moment. The script (either stress or neutral) will be presented for exactly 5 minutes. All measures will be collected immediately following imagery (0) and again at +15 minutes and +30 minutes following imagery exposure. The Stroop task¹³⁸ will be administered at baseline and following imagery only. All saliva will be placed on ice immediately, prior to storing at -20. Participants will then be given a 1-hour break to relax, before repeating the procedure. All procedures will be identical, with the exception of the imagery presented (stress or neutral). The imagery order will be counterbalanced and neither the subject nor the investigator will know the order of imagery presentation prior to the study. Relaxation instructions will be provided to ameliorate any residual effects of imagery. Imagery script development, imagery training and relaxation techniques will be conducted in the week prior to the laboratory sessions (see Human Subjects Section 2.4). 3.7 Follow-up interviews: Face-to-face interviews will be conducted 30 days after outpatient treatment completion. Urine and breathalyzer screens and a daily assessment of alcohol use will be collected using the TLFB method¹³⁰

All 30 day follow-up interviews will be conducted over zoom.

STATISTICS

Data Analyses Plan: Aim1: To evaluate the safety and tolerability of GXR (3mgs/day) in women with AUD. All potential adverse effects from both treatment groups will be recorded twice weekly and classified, per body system and reaction, in a frequency table. Comparisons between treatment groups will be conducted using t-tests, chi-square tests and ANOVAs as appropriate (H1a). Aim2: To determine the preliminary efficacy of 10-week GXR (3mgs/day) versus PLA treatment on outcome measures in women with AUD: All analyses will be conducted using the intent-to-treat sample, and survival analyses will be used to examine medication effects on time to relapse measures. In order to model time intervals between events, reoccurring event-time analysis will be performed ¹³⁹. Hierarchical Linear Models (HLM) will be used to determine the effects of medication on continuous dependent variables, including % days abstinent and number of days in treatment (H2a), as well as secondary outcome variables, including craving, stress, anxiety, mood (H2b). Failures in treatment attendance will be accounted for by treating time as a random effect. Aim 3: To better determine the mechanisms underlying efficacy, by conducting a parallel laboratory study: Linear Mixed Effects (LME) models will examine the effects of medication on all Dependent Variables following stress versus neutral imagery within the laboratory (H3a). In order to elucidate the contribution of GXRrelated stress system changes in

the laboratory on primary drinking outcomes, correlational, regression and survival analyses will be performed as appropriate (H3b).

FUNDING STATUS, DETAILS

NIAAA have stated that they are in the process of issuing a restricted NOA, pending IRB approval.

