Recruitment and consent procedures:

Most assessments will be performed by virtual visits over the secured media site ZOOM with end to end encryption. However, the clinical portion of the recruitment intake process will be performed with the safety precautions using appropriate PPE set forth by the CDC .

AUD treatment-seeking women will all be screened and interviewed by fully trained research staff who will ascertain interest in participating in the current project. If an individual expresses interest, she will receive an explanation of the study, risks, benefits and description of procedures. Subjects will be informed that participation in all components of the research is entirely voluntary and that all information collected will be kept confidential. All women will be asked to sign the research consent form if they wish to participate following resolution of any questions and clear indication that they understand the nature of the study and the consent. After obtaining written informed consent for participation in the study, the study physician will interview all women and review medical and psychiatric data prior to admission.

Confidentiality:

All women who take part in this study will be free to drop out of the study at any time without penalty. All data will be kept confidential except in cases of imminent danger to the participants. Such limits to confidentiality will be clearly explained to participants verbally and in the written consent forms. Confidentiality in regard to collected materials will be maintained via a numbered reference system maintained by the investigators. Subjects' names will appear only on a consent form and a "key" form kept by the PI in locked filing cabinets. Only the project manager and PI will have access to any forms specifying both participant name and subject number. All number coded subjective and biological data will be kept in locked offices with access only to investigators and research staff. Furthermore, good clinical and research practice procedures and HIPAA regulations will be followed. Subjects will be withdrawn from the study if they show severe psychological or symptomatic deterioration. They will subsequently be offered treatment as usual at the CNRU. Alternate treatment recommendations will be made and offered according to the subject's needs and wishes.

Federal Certificate of Confidentiality:

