Contingency Management (CM): CM has been shown to have the largest effect size of all psychosocial therapies for alcohol and substance abuse disorders 155, 156. As such, all women will also receive CM providing them with the opportunity to earn chances of winning dollar prizes of varying magnitudes. The chance of winning prizes will be contingent upon kept appointments, not clean urine toxicology screens. This will decrease the chances of CM masking the effects of the medication. For every two biweekly appointments attended, the chance to draw for a dollar prize will increase by one, making a total of 10 chances if all appointments are met. If appointments are missed the number of prize draw "chances" are reset to one. The participants draw from a prize bowl containing slips of paper stating either a dollar amount or "good job" (50% of the slips). The prizes will be in increments of \$1 (44% of slips), \$20 (6% of slips), and \$100 (1 slip). All slips will be returned to the bowl at the beginning of each draw to maintain probabilities. The total prize amount will be added to the participants check on study completion. If subjects are unable to achieve abstinence within four weeks, they will be offered inpatient treatment or referred to a higher level of care at another facility. If a subject achieves abstinence but has occasional relapses, outpatient treatment will continue until either abstinence is sustained or a higher level of care is clinically indicated.

Importance of the Knowledge to be Gained

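### Outcome assessment after early exit is written only for women who stop attending; the protocol is silent on women withdrawn for deterioration or referred to other care

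*Combined protocol and SAP*

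**What the plan says.** **Women who stop attending.** Section 3.5.3 of the protocol defines the group: "Subjects will be considered drop-outs if they receive two phone calls and two letters inviting them to return". It then provides for them: "We will attempt to assess these early terminators at the time of discontinuation, at the 10 week termination point, and at the follow-up period". It adds: "These women will be withdrawn from the study but considered in the intent-to-treat efficacy analyses".

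**Women who deteriorate.** The Confidentiality paragraph, in the human-subjects part of the protocol, says: "Subjects will be withdrawn from the study if they show severe psychological or symptomatic deterioration". They are then offered usual treatment. No later drinking assessment is mentioned.

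**Women who do not become abstinent, or who relapse.** The Contingency Management paragraph says: "If subjects are unable to achieve abstinence within four weeks, they will be offered inpatient treatment or referred to a higher level of care". For a woman with occasional relapses, "outpatient treatment will continue until either abstinence is sustained or a higher level of care is clinically indicated". The paragraph says neither that these women leave the study nor that TLFB interviews go on.

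**Analysis.** The protocol's Data Analyses Plan says under Aim 2: "All analyses will be conducted using the intent-to-treat sample". Its only remark on incomplete data is that missed attendance is handled by a random effect for time. The SAP, Aim 2, also uses the intent-to-treat sample, in linear mixed models, and has no rule for missing drinking data.

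**The concern.** The one written arrangement for collecting outcomes after early exit is tied to a group defined by non-attendance. The other two routes are triggered by how the woman is doing. A site that follows the text would look for the week-10 drinking of a woman who stops answering calls. It would have no instruction to do so for a woman withdrawn because she deteriorated.

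For that second woman, later frequency, quantity, % heavy-drinking days and % days abstinent may be missing for reasons linked to the outcome. Keeping her in the intent-to-treat sample does not supply those data. A mixed model recovers them only as far as her earlier weeks predict the later ones. If such exits differ between GXR and placebo in number or severity, the estimated effect is biased. More of them on placebo would tend to hide a benefit; more on GXR would tend to hide a harm.

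**Working it through.** **1. The plan's own attrition figure.** The Rationale/overview gives 60 women, up to 30% drop-out, and at least 42 reaching the laboratory session: 60 × (1 − 0.30) = 42, which reproduces. (The Study sample section gives 49 from the same inputs. That equals 70 × 0.70, so it works only if the 10 nicotine-only women are counted. The two figures need reconciling, but this point does not depend on them.) The implied 60 × 0.30 = 18 women are described as leaving after the first few sessions. They are mainly the non-attenders whom 3.5.3 already follows, so 18 is not the number at stake here.

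**2. The exit routes side by side.**

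| Route | Trigger | Said to leave the study? | Later outcome assessment stated? | In intent-to-treat sample? |
|---|---|---|---|---|
| 3.5.3 drop-out | Non-attendance (two calls, two letters) | Yes | Yes, at three times | Yes |
| Confidentiality paragraph | Severe deterioration | Yes | No | Yes, by the general statement |
| Contingency Management paragraph | Not abstinent by four weeks, or relapse needing more care | Not stated | Not stated | Yes, by the general statement |

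**3. Does another provision fill the gap?** The weekly TLFB belongs to the outpatient visit schedule. The 30-day interview (3.7) is timed from completion of outpatient treatment, which a withdrawn woman does not reach. The paragraph on relapse and drop-out concerns women who miss three visits in a row, so it overlaps the 3.5.3 group. None of these names the women in row 2 or settles the position for row 3.

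**4. What could be missing.** Take exit at the end of week 4. Weeks 1–4 are kept and 10 − 4 = 6 of 10 weeks are at risk. A woman not abstinent by then will usually already have had her first-drink event. The loss falls on later frequency, quantity, % heavy-drinking and % abstinent days, and on heavy-drinking events not yet reached. No exit rate is given. For an assumed proportion w of 60 women, woman-weeks missing = 60 × w × 6, out of 600:
- w = 5%: 18 (3%)
- w = 10%: 36 (6%)
- w = 20%: 72 (12%)

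**5. Illustration of the mechanism, not an estimate.** Assume 20% heavy-drinking days in stayers and 60% to 80% in leavers during weeks 5–10, and use observed data only. The arm mean is too low by w × (leaver − stayer):
- w = 10%: 0.10 × 40 = 4 to 0.10 × 60 = 6 points
- w = 20%: 0.20 × 40 = 8 to 0.20 × 60 = 12 points

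The true difference, GXR minus placebo, is (w_GXR − w_placebo) × (leaver − stayer). The observed difference is 0, because stayers are assumed alike.
- Equal exits: true 0, observed 0, no bias
- 10% GXR, 20% placebo: true −4 to −6, observed 0
- 20% GXR, 10% placebo: true +4 to +6, observed 0

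A mixed model using weeks 1–4 would recover part of this if the data are missing at random.

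**6. Can the existing instrument recover the days?** The baseline TLFB already looks back 90 days. The whole treatment period is 10 × 7 = 70 days. From the end of week 4 it is 6 × 7 = 42 days to week 10 and 42 + 30 = 72 days to follow-up. A week-10 interview covers any exit date. A follow-up interview at day 70 + 30 = 100 reaches back to day 10.

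**The case against.** The strongest reply is that much of this is silence, not an instruction to stop. A reader might infer that women withdrawn or referred leave with no further drinking data, and that the worst outcomes are therefore lost. The documents do not support that:

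- The Contingency Management paragraph offers or refers; it does not withdraw. All women with AUD are to attend twice weekly for 10 weeks and visits can be virtual, so referral need not end assessment. A referred woman who then stops attending meets the 3.5.3 definition and gets all three assessments.
- Nothing removes either group from the efficacy analysis. The intent-to-treat statements in the protocol and SAP are general.
- The Confidentiality criterion is deterioration, not relapse as such. Relapse is handled by attempts at re-engagement and continued outpatient care.
- Weekly TLFB data up to exit are kept.
- A woman who enters inpatient care may have more abstinent days afterwards, so even the sign of the missing difference is uncertain.
- Any bias is modest against sampling error. Assuming 30 women per arm and an SD of 20 to 35 points, the standard error is SD × √(2/30), about 5 to 9 points.

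It may also be said that 3.5.3 contradicts itself by withdrawing women whom it then assesses. Read together, its sentences mean off treatment but still followed, so this is loose terminology.

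All of this narrows the point. What remains is that the Confidentiality paragraph uses the same words about leaving the study, without the accompanying promise of later assessment, and that the position of referred women is unstated. Large sampling error does not excuse the gap: the protocol wants these results as the basis for a larger trial, and drinking data never collected cannot be recovered by analysis.

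**Conclusion.** The concern holds in a limited form. Assessment after exit is written for one route only. It is absent for women withdrawn for deterioration, which is the firmer case, and unclear for women offered or referred to other care. Both of these routes are linked to poor outcome, so informative missingness in the later drinking measures is a real risk.

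The size cannot be stated from the documents. They give no rate for these exits, no split by arm and no outcomes after exit. A reader might take the 30% drop-out (18 women) as the measure; it is not, because most of those women fall under the provision that exists. The 4 to 6 points in the illustration rest wholly on assumed exit rates and drinking levels and ignore recovery by the mixed model. Bias in the treatment comparison requires exits that differ between arms in number or severity; if both match, it is zero. The direction is not known. This is a worthwhile and inexpensive improvement, not a defect that by itself invalidates the comparison.

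**What to change.** - **Section 3.5.3:** apply the three assessments to every randomised woman who stops study treatment or outpatient visits before week 10 for any reason, unless she withdraws consent to further contact.
- **Section 3.5.3 and the Confidentiality paragraph:** state that stopping treatment does not end outcome collection, so that being withdrawn is not read as the end of follow-up.
- **Week 10:** take one TLFB back to her last completed one, within the 90-day recall already in use.
- **Records:** note the reason for each exit, and flag days in inpatient or other controlled care so that they are not simply counted as abstinence due to treatment.

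The clinical care rules in the Confidentiality and Contingency Management paragraphs stay as they are.

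The cost is protocol wording plus one or two Zoom or telephone interviews for each woman who stops, with the instrument and remote format already in place. The drawback is longer recall for these women. The SAP is written in the past tense; if follow-up has closed, report early exits by arm and reason, and say for whom drinking data after exit were obtained.

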Data on Adverse Events occurring during the course of conducting this study will be collected, documented and reported to the Stony Brook IRB board and to NIAAA. A summary of all AE's will be prepared annually, by the project PI and the Data Safety Monitoring Board and submitted to the Stony Brook IRB committee and to NIAAA. The Stony Brook IRB requires the re-approval of study protocols at least annually and will not re-approve the protocol without such reports.

Adverse Events (AE) will be defined on the basis of the NIH Guidelines on Data and Safety Monitoring for Intervention Trials. These guidelines define an AE as any reaction, side effect or untoward event that occurs during the course of the clinical trial, whether or not the event is considered related to the study manipulations. A new illness, symptom, unfavorable or unintended sign, or worsening of a pre-existing condition or abnormality will be considered an AE. Stable chronic conditions such as diabetes that are present prior to study entry and do not worsen will not be considered AEs. AEs will include events and symptoms reported by the subjects that are of clinical importance as noted by the study staff. The AE Form will be used for recording the event and any follow-up information. The following Stony Brook IRB/FDA classification of AE "severity" and "attribution" will be used.

Coding of Severity:

0 = No adverse event or within normal limits

1 = Mild adverse event

2 = Moderate adverse event

3 = Severe, resulting in psychiatric or medical hospitalization

4 = Life-threatening adverse event 5 = Fatal adverse event

Coding of Attribution:

- 1 = Unrelated to study interventions
- 2 = Unlikely relationship to study interventions
- 3 = Possible relationship to study interventions
- 4 = Probable relationship to study interventions
- 5 = Definite relationship to study interventions

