Aim1: To evaluate the safety and tolerability of GXR (3mgs/day) in women with Alcohol Use Disorder (AUD). All potential adverse effects from both treatment groups were recorded twice weekly and classified. Descriptive statistics are displayed in a frequency table.

Aim2: To determine the preliminary efficacy of 10-week GXR (3mgs/day) versus PBO treatment on outcome measures in women with AUD: Linear Mixed Effects (LMEs) models were used to analyze data from the intent-to-treat sample where, for all Dependent Variables (% no. of heavy drinking days, % no. of days abstinent, % drinks consumed on any one occasion, alcohol craving, depressive symptomatology, anxiety and emotion regulation), the Between Group Factors of Group (GXR, PBO) and Within Group Factors of Time-points (12-weeks), represented the Fixed Effects and Subjects represented the Random Effects. Demographic and drug use variables differing between Treatment Groups and associated with the Dependent Variables were entered as covariates into the models and a Compound Symmetry covariance structure was applied to the model. Descriptive statistics were additionally conducted on % no. of negative urines collected across the trial.

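### No SAFTEE is specified before the first dose, so adverse events cannot be sorted systematically into new, worsened or pre-existing, and the Aim 1 table loses precision and a valid absolute incidence.

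*Combined protocol and SAP*

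**What the plan says.** **When SAFTEE is given.** The protocol's Data Safety list, under 3.5.3 Outpatient Assessments, has "Systematic Assessment of Treatment Emergent Events (SAFTEE): every week to assesses the severity and duration of potential physical or health problems". The weekly visit schedule lists it first: "SAFTEE sheet – documenting any adverse effects". It is not named in the Screening & intake battery or in the COVID-19 versions of Intake 1 and Intake 2.

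**What does get a baseline.** The secondary-outcome scales, also under 3.5.3, are introduced with "The following measures will be administered upon admission and twice weekly", and the drinking calendar interview is taken at baseline and then weekly. At Intake 2 the woman completes unnamed questionnaires before the first dose. After the sentence on that dose the text adds "Questionnaires and surveys will be conducted and timeline follow back will be obtained", again naming no instrument except the calendar interview.

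**What counts as an adverse event.** The section on monitoring and reporting AEs and SAEs opens with a broad definition that ignores relatedness. It continues: "A new illness, symptom, unfavorable or unintended sign, or worsening of a pre-existing condition or abnormality will be considered an AE". Stable chronic conditions present before entry are excluded. The section also says: "AEs will include events and symptoms reported by the subjects that are of clinical importance as noted by the study staff".

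**What Aim 1 reports.** The protocol's analysis plan compares the arms with t-tests, chi-square tests and ANOVAs. The SAP says "All potential adverse effects from both treatment groups were recorded twice weekly and classified" and gives descriptive statistics in a frequency table.

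**The concern.** A rule that counts new or worsened symptoms can be applied consistently only if symptoms were recorded before dosing on the same instrument. Here the first SAFTEE is an on-treatment form.

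The population makes this more than a formality. Inclusion requires a positive toxicology screen on admission or a recent detox. The initial reactions that the risk section names for guanfacine are fatigue, sedation, light-headedness, dizziness and vertigo, complaints that such women may bring with them. The protocol's own pilot study of the immediate-release form reports fatigue as the commonest side effect, with symptoms clearing within the first two weeks. A first on-treatment form therefore falls where early drug effects are expected and cannot stand in for a baseline.

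Safety and tolerability are Aim 1 and H1. If pre-existing complaints enter the table, the reported incidence in each arm is not an incidence of treatment-emergent events, and the contrast between arms carries avoidable noise.

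**Working it through.** The documents give no adverse-event rate, effect size, alpha or power for Aim 1, so there is no stated figure to reproduce. The question is what a missing baseline does to the table.

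**Inputs**
- From the documents: 60 women with AUD, randomised to GXR or placebo. The allocation ratio is not stated; 1:1 is assumed, giving n = 30 per arm. Drop-out is ignored.
- Assumed: pre-dose prevalence of a symptom, b = 20% or 40% in both arms; new onset among women without it, q = 5% on placebo and 30% on GXR; women with the symptom before dosing report it again on treatment; no pre-existing symptom worsens.

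**Formulas**
- Count of any report, no baseline available: p = b + (1 − b)q
- Count of new onset, baseline available: p = (1 − b)q
- The difference between arms is (1 − b)(q_GXR − q_placebo) under both counts, because b cancels.
- Standard error of the difference: √[p₀(1 − p₀)/30 + p₁(1 − p₁)/30]

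**Results**

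| b | Count | Placebo | GXR | Difference | SE (points) | Exact Fisher power, two-sided 5% |
|---|---|---|---|---|---|---|
| 20% | any report | 24% | 44% | 20 | 12.0 | 28% |
| 20% | new onset | 4% | 24% | 20 | 8.6 | 45% |
| 40% | any report | 43% | 58% | 15 | 12.8 | 15% |
| 40% | new onset | 3% | 18% | 15 | 7.7 | 26% |

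Example, b = 40%, any report: 0.40 + 0.60 × 0.05 = 0.43 and 0.40 + 0.60 × 0.30 = 0.58; SE = √[(0.43 × 0.57 + 0.58 × 0.42)/30] = √(0.4887/30) = 0.128.

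**Reading the table**
1. The expected difference does not change: 44 − 24 = 24 − 4 = 20 points, and 58 − 43 = 18 − 3 = 15 points.
2. Precision does. Without a baseline the standard error is 12.0/8.6 = 1.4 times as large at b = 20%, and 12.8/7.7 = 1.7 times at b = 40%.
3. Absolute incidence is inflated in both arms. On GXR it is 44/24 = 1.8-fold and 58/18 = 3.2-fold; on placebo it is 24% against 4%, and 43% against 3%.
4. Chance imbalance in pre-dose prevalence has a 95% range of ±1.96 × √[2b(1 − b)/30]: about ±20 points at b = 20% and ±25 points at b = 40%. Without a pre-dose form it can be neither seen nor adjusted for.

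**A second set of assumptions.** With new onset of 10% against 40% and b = 30%, approximate power is 0.37 for any report and 0.58 for new onset. Under equal rates in the two arms, with b from 0 to 50%, the exact false-positive rate of an uncorrected chi-square test on the any-report count is 0.048 to 0.054, so the missing baseline does not create spurious drug effects.

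**The case against.** **The placebo arm already does the separating.** A reader might infer that Aim 1 cannot tell GXR effects from symptoms the women brought in, or that a true excess would be hidden. The documents do not support that. The trial is randomised, double-blind and placebo-controlled, and adverse effects are recorded in both arms. Background symptoms have the same expected frequency in each, and the expected difference survives intact. This objection stands and limits the point to precision, classification and absolute incidence.

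**The any-report column is a worst case.** It treats the new-or-worsened rule as if it were never applied. Staff could apply it in part from the woman's recall, from the duration that SAFTEE records, and from the intake physical examination, bloods, EKG, physician review and mood and anxiety scales. That is fair, and the true position probably lies between the two columns. None of these sources is a systematic side-effect inventory, however, and no text links them to adverse-event classification.

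**SAFTEE might be among the unnamed Intake 2 questionnaires.** It might; the text neither says so nor rules it out.

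**Power is a weak argument here.** The SAP plans description only, and in the main illustration power stays at or below 45% even with a baseline. I agree. The power column only expresses the loss of precision.

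**The clinical-importance sentence.** It could be read as a filter that drops mild events. But it says such symptoms are included, it follows a broad definition, mild is an explicit severity code, and no text says that it filters the Aim 1 table. It has no criteria, so it is a wording ambiguity and nothing more.

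**Conclusion.** The point holds as a cheap improvement to Aim 1. No pre-dose SAFTEE is specified, although the adverse-event definition needs one. As a result, treatment-emergent status cannot be assigned systematically, absolute incidence in either arm may include pre-existing symptoms, the contrast is less precise, and chance baseline imbalance cannot be checked. The between-arm difference remains unbiased.

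In the illustration the standard error is 1.4 to 1.7 times as large and GXR incidence 1.8 to 3.2 times as large as with a baseline, with no change in the expected difference. These sizes rest on assumed prevalence and onset rates, 30 per arm, no drop-out, no worsening of pre-existing symptoms, and no use of recall or other records to sort events. If pre-existing prevalence is near zero, the loss is near zero.

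**What to change.** 1. Give SAFTEE once at Intake 2, before the first dose, and name it in the intake schedule.
2. Define a treatment-emergent event as a SAFTEE item absent before dosing, or more severe on treatment than before dosing.
3. In the Aim 1 table, count women with at least one such event by arm, with an exact 95% confidence interval for the difference. Counting women also stops a symptom repeated across visits from being counted many times.
4. Tabulate all SAFTEE items regardless of staff-judged importance, and say that the clinical-importance sentence does not restrict this table.
5. In the same edit, reconcile weekly SAFTEE administration with the twice-weekly recording stated under Aim 1.

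**Cost.** One extra form per woman at an existing visit, plus wording in the protocol and SAP. The SAP is written in the past tense, so for some or all women the pre-dose form may no longer be obtainable. For them, label the counts as without baseline, show both arms side by side with the interval for the difference, and do not present either arm's figure as a treatment-emergent incidence.
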